6.3. Randomization Inclusion Criteria

At the end of the Run-in period (Visit 2), study participants must fulfil the following additional criteria in order to be randomized into the study and enter the treatment period:

CONFIDENTIAL

- 1. Asthma Control Questionnaire (ACQ): ACQ-5 score ≥ 1 and ≤ 4 at Visit 2.
- 2. **eDiary Compliance:** Compliance with completion of the eDiary reporting defined as completion of all questions/assessments on ≥4 of the last 7 days during the run-in period.

6.4. Randomization Exclusion Criteria

Participants meeting any of the following criteria **must not** be randomized to double-blind study medication at Visit 2:

- 1. Clinically significant and abnormal laboratory finding at Screening (Visit 1): Evidence of clinically significant abnormal laboratory tests during screening which are still abnormal upon repeat analysis and are not believed to be due to disease(s) present. Each Investigator will use his/her own discretion in determining the clinical significance of the abnormality.
- 2. **12-lead ECG over-read**: Evidence of clinically significant abnormal ECG findings (Table 2) at Screening (Visit 1).
- 3. **24-Hour Holter Monitoring**: An abnormal and significant finding from 24-hour Holter monitoring at Screening (Visit 1). Investigators will be provided with Holter reviews conducted by an independent cardiologist to assist in evaluation of subject eligibility. Specific findings that preclude subject eligibility are listed in Table 2. The study investigator will determine the medical significance of any Holter abnormalities not listed in Table 2.
- 4. **Liver function** at Screening (Visit 1)
 - ALT >2x upper limit of normal (ULN) and bilirubin >1.5xULN (isolated bilirubin >1.5xULN is acceptable if bilirubin is fractionated and direct bilirubin <35 %).
 - Current or chronic history of liver disease, or known hepatic or biliary abnormalities (with the exception of Gilbert's syndrome or asymptomatic gallstones.
- 5. **Asthma exacerbation:** Participants with ongoing asthma exacerbation at the time of Visit 2.

Note: At the Investigator's discretion, participants with an ongoing asthma exacerbation at Visit 2 may be re-screened \geq 2 weeks after Visit 2. In such cases, the full screening process (i.e. all Visit 0, 1 and Visit 2 assessments) must be repeated.

- 6. **Severe airflow obstruction:** a pre-bronchodilator FEV1 <50 % predicted of normal value at Visit 2. Predicted values will be based upon GLI [Quanjer, 2012] equations for spirometry reference values.
- 7. **Positive pregnancy test** at Visit 0, Screening (Visit 1) or Visit 2.
- 8. **Ongoing or recurrent infections** requiring systemic antibiotics.

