8. DISCONTINUATION CRITERIA

8.1. Discontinuation of Study Treatment

Participants that permanently stop study treatment are encouraged to remain in the study. Participants have the right to discontinue study treatment before the end of the study. A participant may also be asked to discontinue study treatment at the Investigator's discretion.

Participants who withdraw from study treatment prematurely (for any reason) should, where possible, continue to be followed-up until the completion of the Safety Follow-up assessments:

• For participants who discontinue IP early, but have not withdrawn consent to participate in the study, an early withdrawal (EW) visit will be performed 4 weeks after the last dose of blinded study treatment. These participants should continue in the study and complete all assessments at the remaining protocol-defined visits until their EW visit. Participants should resume regular treatment for their asthma, as determined by the investigator. Three Follow-up visits will then be performed 4, 8, and 12 weeks after the EW visit for safety assessments.

CONFIDENTIAL

• Participants who discontinue IP early and withdraw consent to participate in the study should complete as many assessments planned for the EW visit as possible.

If this is not possible, the Investigator must encourage the participant to participate in as much of the study as they are willing (or able) to.

A participant may be withdrawn from study treatment at any time. A reason for premature discontinuation of study treatment (e.g., AE, lack of efficacy [including loss of asthma control], protocol deviation, Investigator discretion, consent withdrawn etc.) must be captured in the eCRF.

A participant must be withdrawn from study treatment if any of the following stopping criteria are met:

- 1. Liver Chemistry: Meets any of the protocol-defined liver chemistry stopping criteria.
- 2. QTc: Meets any of the protocol-defined stopping criteria.
- 3. Pregnancy: Positive pregnancy test.
- 4. Participant meets at least one of the following criteria for 'loss of asthma control':
 - ACQ-5 score increase from baseline (measured at Visit 2) \geq 0.5 point.
 - Pre-bronchodilator FEV1 decrease from baseline (measured at Visit 2) >7.5 %.
 - Inability to continue inhaled corticosteroid titration which is assessed and determined by the investigator at any time point following randomization, including on scheduled clinic visits.

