12.7. Appendix 7: Liver Safety: Required Actions and Follow-up Assessments

Phase II liver chemistry stopping and increased monitoring criteria have been designed to assure participant safety and evaluate liver event etiology

Phase II liver chemistry stopping criteria and required follow up assessments

Liver Chemistry Stopping Criteria				
ALT-absolute	ALT ≥ 5xULN	ALT ≥ 5xULN		
ALT Increase	ALT ≥ 3xULN persists for ≥4 weeks			
Bilirubin ^{1, 2}	ALT $\geq 3xULN$ and bilirubin $\geq 2xUL$.N (>35% direct bilirubin)		
INR ²	ALT ≥ 3xULN and INR>1.5, if INR	measured		
Cannot Monitor	ALT ≥ 3xULN and cannot be monitored	ed weekly for 4 weeks		
Symptomatic ³	ALT ≥ 3xULN associated with syn related to liver injury or hypersensi	nptoms (new or worsening) believed to be tivity		
	Required Actions and Follo	w up Assessments		
	Actions	Follow Up Assessments		
• Immediately	discontinue study treatment	Viral hepatitis serology ⁴		
 Report the event to GSK within 24 hours Complete the liver event CRF and complete an SAE data collection tool if the event also meets the criteria for an SAE² 		 Obtain INR and recheck with each liver chemistry assessment until the transaminases values show downward trend. 		
Perform liver chemistry event follow up assessments		 Obtain blood sample for pharmacokinetic (PK) analysis within 1 week after the liver event⁵ 		
Monitor the participant until liver chemistries resolve, stabilize, or return to within baseline (see MONITORING below)		Serum creatine phosphokinase (CPK) and lactate dehydrogenase (LDH).		
Do not restart/rechallenge participant with study treatment unless allowed per protocol and GSK Medical Governance approval is granted (see below)		 Fractionate bilirubin, if total bilirubin≥2xULN 		
		Obtain complete blood count with differential to assess eosinophilia		
If restart/rechallenge not allowed per protocol or not granted, permanently discontinue study treatment and continue participant in the study for any protocol specified follow up assessments		 Record the appearance or worsening of clinical symptoms of liver injury, or hypersensitivity, on the AE report form Record use of concomitant medications 		

MONITORING:

For bilirubin or INR criteria:

- Repeat liver chemistries (include ALT, AST, alkaline phosphatase, bilirubin) and perform liver event follow up assessments within 24 hrs
- Monitor participants twice weekly until liver chemistries resolve, stabilize or return to within baseline

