- 4. Includes: Hepatitis A IgM antibody; Hepatitis B surface antigen (HbsAg) and Hepatitis B Core Antibody (IgM); Hepatitis C RNA; Cytomegalovirus IgM antibody; Epstein-Barr viral capsid antigen IgM antibody (or if unavailable, obtain heterophile antibody or monospot testing); Hepatitis E IgM antibody
- 5. PK sample may not be required for participants known to be receiving placebo or non-GSK comparator treatments.) Record the date/time of the PK blood sample draw and the date/time of the last dose of study treatment prior to PK blood sample draw on the CRF. If the date or time of the last dose is unclear, provide the participant's best approximation. If the date/time of the last dose cannot be approximated OR a PK sample cannot be collected in the time period indicated above, do not obtain a PK sample. Instructions for sample handling and shipping are in the SRM.

Phase II liver chemistry increased monitoring criteria with continued therapy

Liver Chemistry Increased Monitoring Criteria – Liver Monitoring Event				
Criteria	Actions			
ALT ≥3xULN and <5xULN and bilirubin <2xULN, without symptoms believed to	Notify the GSK medical monitor within 24 hours of learning of the abnormality to discuss participant safety.			
be related to liver injury or	Participant can continue study treatment			
hypersensitivity, and who can be monitored weekly for 4 weeks	Participant must return weekly for repeat liver chemistries (ALT, AST, alkaline phosphatase, bilirubin) until they resolve, stabilise or return to within baseline			
	If at any time participant meets the liver chemistry stopping criteria, proceed as described above			
	If, after 4 weeks of monitoring, ALT <3xULN and bilirubin <2xULN, monitor participants twice monthly until liver chemistries normalize or return to within baseline.			

References

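### The liver exclusion at randomisation joins its two limits with 'and', which empties its own bilirubin exception and, read literally, leaves no stand-alone ALT limit at entry

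*Protocol*

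**What the plan says.** Section 6.4 lists findings any one of which means a participant must not "be randomized to double-blind study medication at Visit 2". Item 4, on liver function at Screening, has two bullets. The first reads "ALT >2x upper limit of normal (ULN) and bilirubin >1.5xULN (isolated bilirubin >1.5xULN is acceptable if bilirubin is fractionated" with a direct share under 35%). The second covers "Current or chronic history of liver disease, or known hepatic or biliary abnormalities", with exceptions for Gilbert's syndrome and asymptomatic gallstones.

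Item 1 of the same list covers clinically significant laboratory abnormalities that persist on repeat and are not attributed to disease already present. It adds: "Each Investigator will use his/her own discretion in determining the clinical significance of the abnormality". Exclusion 13 in section 6.2 names hepatic disease among conditions that rest on the investigator's opinion.

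On treatment, section 8.1 makes withdrawal mandatory for a participant who "Meets any of the protocol-defined liver chemistry stopping criteria" (section 8.1.1 words this more softly, as something to consider). In Appendix 7, ALT of 5xULN or more is a stopping criterion by itself, whatever the bilirubin, and the required action is immediate discontinuation. Another stopping row is "ALT ≥ 3xULN persists for ≥4 weeks". A separate table allows continued treatment with weekly monitoring for "ALT ≥3xULN and <5xULN and bilirubin <2xULN, without symptoms believed to" be related to liver injury or hypersensitivity, provided weekly monitoring is possible.

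The exclusion wording is the same in all three protocol versions in the file, so it is current text and two amendments left it unchanged.

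**The concern.** An exception should remove something that the main rule would otherwise catch. The bracket says when a bilirubin rise without an ALT rise may be tolerated. If exclusion needs both rises, that case is already admitted and the conditions on fractionation and direct share do no work. The bracket therefore implies two separate limits, while the connective states one joint limit.

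The two readings give opposite decisions for a participant with raised ALT and normal bilirubin. Section 6 permits no waivers, so the wording decides eligibility and sites may apply it differently. On the literal reading, someone whose screening ALT already meets a mandatory stopping level can be given a first infusion of a new antibody unless judgement or a known liver condition intervenes.

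**Working it through.** The protocol gives no figure to reproduce here. The check is logical.

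**Inputs.** Limits of ALT >2xULN and bilirubin >1.5xULN, with the bracket excusing isolated bilirubin if it is fractionated and direct is <35% (section 6.4, item 4). Stopping at ALT ≥5xULN alone (Appendix 7).

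**Rules compared.** Let A mean ALT >2xULN and B mean bilirubin >1.5xULN.
- 'And' rule: exclude if A and B.
- 'Or' rule: exclude if A or B.
- Bracket: admit if B and not A, fractionated, and direct <35%.

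**Why the bracket is empty under 'and'.** The bracket applies only when A is false. The 'and' rule excludes only when A is true. The two sets never overlap, so the bracket can change no decision.

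**Eight cases** (ALT and bilirubin in xULN):

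| ALT | Bilirubin | Direct | 'and' | 'and' + bracket | 'or' | 'or' + bracket |
|---|---|---|---|---|---|---|
| 1 | 1 | 20% | admit | admit | admit | admit |
| 2.5 | 1 | 20% | admit | admit | exclude | exclude |
| 4 | 1 | 20% | admit | admit | exclude | exclude |
| 6 | 1 | 20% | admit | admit | exclude | exclude |
| 1 | 2 | 20% | admit | admit | exclude | admit |
| 1 | 2 | 50% | admit | admit | exclude | exclude |
| 1 | 2 | not fractionated | admit | admit | exclude | exclude |
| 6 | 2 | 50% | exclude | exclude | exclude | exclude |

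The bracket changes 0 of 8 decisions under 'and' and 1 of 8 under 'or' (isolated bilirubin of 2xULN with 20% direct, which it is meant to admit).

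**Wider grid.** ALT 1, 2, 2.5, 3, 5, 8; bilirubin 1, 1.5, 1.6, 2, 3; direct 20, 34, 35, 36, 60%. That is 6 × 5 × 5 = 150 combinations. Under 'and' the bracket changes 0 of 150. Under 'or' it changes those with ALT 1 or 2, bilirubin 1.6, 2 or 3, and direct 20 or 34%: 2 × 3 × 2 = 12.

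**Entry against stopping, for isolated ALT with bilirubin at 1xULN:**
- ALT 2.5xULN: admitted under 'and'; below every Appendix 7 level.
- ALT 4xULN: admitted under 'and'. Without symptoms, Appendix 7 allows treatment with weekly monitoring. It becomes a stop only if it persists for 4 weeks or cannot be monitored weekly.
- ALT 6xULN: admitted under 'and'; an immediate stop under Appendix 7, since 6 ≥ 5.

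**After the change to 'or'.** Every Appendix 7 stopping row needs ALT of at least 3xULN. Since 3 > 2, a stand-alone entry limit of ALT >2xULN excludes anyone whose screening ALT meets any of them.

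**Other entry criteria.** Item 1 of section 6.4, the second bullet of item 4, and exclusion 13 contain no numeric ALT limit.

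**The case against.** The strongest reply is that the line has an evident intended meaning. In a list of excluding findings, 'and' can simply name two findings, and a site that gives the bracket a function arrives at separate limits. On that view the bracket is redundant under the literal reading rather than contradictory, and this is a clarification.

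The intent is indeed probably two limits. But Appendix 7 uses the same construction, ALT and bilirubin joined by 'and', as a joint condition for possible severe liver injury, so a site following the protocol's own usage would read it literally.

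Second, other criteria can reach a marked ALT rise. An investigator would struggle to call ALT of 5xULN or more clinically insignificant under item 1, and a confirmed rise might count as a known hepatic abnormality. This stands in part: many such cases would be caught. None would be caught by a fixed limit, and item 1 also lets through abnormalities attributed to disease already present.

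Third, liver chemistry is repeated at Visit 2 and at Weeks 2 and 4. That should reveal a persistent ALT of 5xULN or more before the second dose at Week 4. It does not secure the first dose, because the Visit 2 sample goes to a central laboratory and need not be reported before infusion.

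Finally, the eight cases show how the rules differ, not how often the difference would matter. That is correct.

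**Conclusion.** The concern holds. The criterion is wrong as written: its bracket has no effect under 'and', and on the literal reading no entry criterion gives a numeric ALT limit. An isolated screening ALT of 5xULN or more, which requires stopping on treatment, is then kept from a first infusion only by judgement or by a known liver condition. The claim does not extend to symptom-free ALT of 3 to <5xULN with bilirubin <2xULN as an immediate stop, because Appendix 7 allows monitored treatment there.

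The logical result needs no assumption beyond the literal meaning of 'and'. Its practical frequency cannot be stated, since the protocol reports no screening ALT distribution. It is a safety and eligibility defect and leaves the sample size calculation and the analysis methods untouched. It should be corrected, though a drafting slip is the likely cause and many sites would act sensibly anyway.

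**What to change.** In section 6.4, item 4, first bullet, replace 'and' between the two limits with 'or': exclude for ALT >2xULN, or for bilirubin >1.5xULN, keeping the existing exception for isolated bilirubin that is fractionated with direct bilirubin <35%. Each limit then excludes alone, the bracket does its job, and nobody whose screening ALT meets an Appendix 7 stopping level can be randomised. Deleting the bracket and keeping 'and' would not be enough, because the ALT gap would remain.

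The cost is one word in one protocol line, and possibly a few more participants lost before randomisation among the approximately 300 screened. That number cannot be estimated from the protocol.

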6.5. Lifestyle Restrictions

No lifestyle restrictions are required for this study.

6.6. Pre-Screening/Screening/Run-in/Randomization Failures

A participant will be assigned a participant number at the time the informed consent is signed at Visit 0.

The study site will be responsible for reporting pre-screen failures. The following information will be collected in the eCRF for participants who are pre-screen failures:

- Demographic information including race, age and gender
- Participant number
- Serious Adverse Event information only for any SAE considered as related to study participation

For the purposes of this study, pre-screening failures, screening failures, run-in failures and randomization failures will be defined as follows:

- **Pre-screening failures:** those participants that sign the informed consent document but do not have a Screening (Visit 1) procedure.
- **Screening failures:** those participants that complete at least one Screening (Visit 1) procedure but do not enter the run-in period.
 - A participant who completes Visit 1 assessments and is dispensed the study medication for the run-in period is considered to have entered the run-in period.
- **Run-in failures:** those participants that enter the run-in period but do not have any Visit 2 procedures.
- **Randomization failures:** those participants that complete at least one Visit 2 procedure but do not enter the double-blind study treatment period.

Any participant who completes the run-in period and then meets the randomization criteria and receives the double-blind study treatment at Visit 2 is considered to have entered the treatment period.

A minimal set of screen failure information is required to ensure transparent reporting of screen failure participants to meet the Consolidated Standards of Reporting Trials (CONSORT) publishing requirements and to respond to queries from regulatory authorities. Minimal information includes demography, screen failure details, eligibility criteria, and any serious adverse events (SAEs).

207597

Rescreening is only allowed in exceptional circumstances of technical errors and with prior approval from the GSK study team. Participants who are excluded due to an ongoing asthma exacerbation at Visit 2 (Randomization exclusion criterion 5) may be rescreened ≥2 weeks after Visit 2, at the investigators discretion. Rescreened participants will be assigned a new participant number.

7. TREATMENTS

Study treatment is defined as any investigational treatment(s), marketed product(s), placebo, or medical device(s) intended to be administered to a study participant according to the study protocol.

7.1. Treatments Administered

Study Treatment Name:	GSK3772847	Placebo	Fluticasone Propionate/Salmeterol	Fluticasone Propionate
Dosage formulation:	50mg/mL GSK377284, 15 mM Sodium Phosphate, 8.5% [w/v] Sucrose, and 0.04% [w/v] Polysorbate 20, pH 7.3.		DISKUS- 60 doses per device	DISKUS- 60 doses per device
Unit dose strength(s)/Dosage level(s):	10 mg/kg	Commercially sourced sterile normal saline	500/50 mcg per actuation	500, 250, 100 and 50 mcg per actuation
Route of Administration	IV infusion	IV infusion	Inhaled	Inhaled
Dosing instructions:	GSK3772847 for injection will require further reconstitution and dilution at the study site prior to administration: dilution between 10 and 30 mg/mL may be accomplished by using commercially sourced sterile normal saline		Twice daily; once in the morning and once in the evening	Twice daily; once in the morning and once in the evening

Study Treatment Name:	GSK3772847	Placebo	Fluticasone Propionate/Salmeterol	Fluticasone Propionate
Packaging and Labeling	Study Treatment will be provided as 100mg/vial, white to yellow, uniform lyophilized cake in a 5ml clear glass vial with 20mm closure sealed by red metal and yellow overseal. Each container will be labeled as required per country requirement.	Commercially sourced sterile normal saline will be sourced by the site	Diskus Inhaler with 60 doses (1 strip with 60 blisters per strip) Each container will be labeled as required per country requirement.	Diskus Inhaler with 60 doses (1 strip with 60 blisters per strip) Each container will be labeled as required per country requirement.

7.1.1. Description of Albuterol/Salbutamol

Albuterol/salbutamol via metered-dose inhaler (MDI) will be issued for reversibility testing at Screening (Visit 1). An albuterol/salbutamol MDI for as needed (prn) use throughout the study will be dispensed starting at Visit 1; at the Investigator's discretion, more than one MDI may be dispensed at any one time. Albuterol/salbutamol will be sourced from local commercial stock. The contents of the label will be in accordance with all applicable regulatory requirements.

7.1.2. DISKUS Return

DISKUS inhalers containing FP/Salmeterol and FP will be dispensed to a participant during their visit to the study clinic (as applicable). The participant must return all dispensed inhalers at the subsequent clinic visit. The schedule for dispensing and collecting FP/Sal and FP is provided in the SoA (Section 2).

All used and unused FP/Sal, FP will be returned to GSK at the end of the study to be available for disposal. In some instances, for sites outside the United States (US), study supplies will be disposed of locally either by the site, the country medical department or

third-party vendor. Detailed instructions for the return of the study drug can be found in the Study Reference Manual (SRM).

If any DISKUS inhaler fails to function properly, the participant should return to the clinic as soon as possible to obtain a new inhaler. The site will use the Interactive Web Response System (IWRS) (RAMOS NG) to obtain a new treatment pack number for the participant and dispense a new study treatment kit from the site's study treatment supply as instructed by the IWRS. Details of the failure will be documented in the eCRF. Additional information on how to handle medical device incidents can be found in the SRM.

7.2. Dose Modification

There are no dose modifications planned for this protocol.

7.3. Method of Treatment Assignment

Participants will be assigned to study treatment in accordance with the randomization schedule. The randomization code will be generated by GSK using a validated computerized system. Participants will be randomized using an interactive web response system (IWRS) RAMOS NG. The study will use central-based randomization to allocate treatments. Once a randomization number is assigned to a participant it cannot be reassigned to any other participant in the study.

Following the 2-week Run-in period and subject to satisfying all eligibility criteria, participants will be randomized 1:1 to one of the following double-blind treatments for the duration of the Treatment Period:

- GSK3772847 (10 mg/kg) administered intravenously
- Placebo administered intravenously

The duration of the Treatment Period for each participant is 16 weeks. Each Investigator will be provided with sufficient supplies to conduct the trial. Additional treatment kits will be supplied as needed to the sites. Details of how to use the IWRS system (RAMOS NG) to randomize participants and manage study treatment supplies (including dispensing) is provided in the RAMOS NG manual and SRM.

